8.5 Samples (if applicable)

Not applicable

8.6 Discontinuation/withdrawal of participants

A participant may be withdrawn from trial whenever continued participation is no longer in the participant's best interests, but the reasons for doing so must be recorded. Reasons for discontinuing the trial may include:

disease progression whilst on therapy

- intercurrent illness
- patients withdrawing consent or Personal/Nominated Consultees withdrawing assent for participants lacking capacity
- persistent non-compliance to protocol requirements.

The decision to withdraw a participant from treatment will be recorded in the CRF and medical notes. If a participant explicitly states they do not wish to contribute further data to the trial their decision must be respected and recorded in the CRF and medical notes.

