A group at UCL, led by [name], have developed a manualised individual CST (iCST) intervention for people with dementia (without ID (13, 14). They have recently completed a multicentre randomised controlled trial of iCST delivered by family carers, compared to "treatment as usual" in 356 carers and individuals with dementia (15). The intervention comprises 75 sessions (each session was 30 minutes, given 3 times a week, over 25 weeks). This study found that iCST did not improve cognition or quality of life for people with dementia and it did not improve carers' physical or mental health. However, there was some improvement in the caregiving relationship and in carers' health related quality of life. Possible reasons for the lack of differences in the treatment and control groups in relation to cognition and quality of life could be attributed to the poor compliance rate. Only 51% of the dyads completed more than 30 sessions out of 75 and 22% did not complete any sessions. Adherence analyses found that people with dementia who completed more sessions showed improved quality in the caregiving relationship and carers reported lower depressive symptoms at 26 weeks. Qualitative data suggested that people with dementia and their carers experienced better communication as a result of iCST.

No studies have examined the feasibility of individual CST in people with ID with or without dementia. We aim to work closely with our UCL colleagues in developing individual CST for people with ID and dementia.

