11.6.2 Primary outcome analysis

This is a feasibility study and therefore we are interested in examining the data in relation to recruitment. This will include information on how many participants were approached and agreed to be screened; how many met the eligibility criteria and agreed to take part and how many completed the study, or dropped out.

We do not anticipate that there will be any differences in between the intervention group and control with respect to the primary outcome as this is a feasibility study. We will calculate the changes in the mean and standard deviation between the two groups using Analysis of Covariance (ANCOVA), adjusting for the baseline score on the primary cognitive measure.

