11.6.4 Sensitivity and other planned analyses

No sensitivity analysis will be conducted.

12 Record keeping and archiving

At the end of the trial, all essential documentation will be archived securely by the CI for a minimum of 20 years from the declaration of end of trial.

Essential documents are those which enable both the conduct of the trial and the quality of the data produced to be evaluated and show whether the site complied with all applicable regulatory requirements.

The sponsor will notify sites when trial documentation can be archived. All archived documents must continue to be available for inspection by appropriate authorities upon request.

13 Oversight Committees

There will be a Trial Management Group.

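### Section 8.6 does not separate stopping iCST from leaving the trial, so CAMCOG-DS data may be lost because of decline, with no sensitivity analysis to show the effect

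*Protocol*

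**What the plan says.** Section 8.6 opens at the level of the trial: "A participant may be withdrawn from trial whenever continued participation is no longer in the participant's best interests". The list that follows is introduced by "Reasons for discontinuing the trial may include" and includes "disease progression whilst on therapy" and "persistent non-compliance to protocol requirements". The next paragraph changes level: "The decision to withdraw a participant from treatment will be recorded in the CRF and medical notes". The only sentence on later data says that an explicit refusal to contribute more must be respected. No section says whether a participant withdrawn for another reason is still assessed.

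The primary outcome is change in cognition on the CAMCOG-DS (11.1), analysed by ANCOVA adjusted for the baseline score (11.6.2). Section 11.6.4 states "No sensitivity analysis will be conducted". Secondary objective 2 in section 4 is to obtain the mean and SD of the primary outcome to size a larger trial. Secondary objective 1 includes drop-out and adherence among the feasibility measures.

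**The concern.** Progression of dementia is, in large part, decline in what the CAMCOG-DS measures. A rule that lets a participant leave the trial for progression lets the outcome decide whether it is observed.

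Exposure to the rule is also unequal. Controls have usual care only (7.1). The iCST arm has 40 sessions over 20 weeks, a diary, recorded sessions and support visits at least monthly (7.1, 8.3, 8.4). It therefore has a therapy to be on, more requirements to miss, and more occasions on which decline or missed sessions would be noticed.

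At stake are the figures this trial exists to supply: the between-arm difference and SD for the next trial, and clean counts of drop-out and adherence. Non-adherence is foreseeable. Of the earlier iCST trial in people without ID, section 3 reports: "Only 51% of the dyads completed more than 30 sessions out of 75 and 22% did not complete any sessions".

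**Working it through.** **1. The text.** Within 8.6, the opening sentence and the list concern the trial, the recording sentence concerns treatment, and the refusal sentence concerns data. A site could apply the section in either of two ways: stop iCST and keep assessing, or stop everything. Nothing elsewhere settles it.

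**2. A figure to reproduce.** None. Section 11.3 gives no power, SD, effect size or drop-out rate. What follows is illustration.

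**3. Inputs.** From the protocol: 20 per arm, baseline-adjusted ANCOVA. Assumed: true effect zero; baseline and follow-up standard normal with correlation ρ of 0.5, 0.7 or 0.9; the 5%, 10% or 20% with the largest decline removed from the iCST arm; controls removed at none, half or all of that rate.

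**4. Bias from removal for progression.** Large-sample simulation, 200,000 per arm. Ranges run over the three correlations. Bias is in outcome SD, positive favouring iCST. The SD ratio is residual SD after removal divided by its true value.

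| iCST removed | Controls removed | Bias | SD ratio |
|---|---|---|---|
| 5% | none | 0.045 to 0.085 | 0.954 to 0.962 |
| 10% | none | 0.087 to 0.154 | 0.933 to 0.945 |
| 20% | none | 0.149 to 0.277 | 0.908 to 0.924 |
| 5% | half rate | 0.017 to 0.035 | 0.923 to 0.935 |
| 10% | half rate | 0.037 to 0.070 | 0.877 to 0.901 |
| 20% | half rate | 0.067 to 0.123 | 0.815 to 0.843 |
| 5% to 20% | same rate | within 0.004 of 0 | 0.770 to 0.920 |

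Hand check for removal in one arm: bias ≈ (1+ρ) × √((1−ρ)/2) × φ(z)/(1−p), where z is the normal quantile for the removed fraction p. At ρ = 0.7 and p = 0.10 this is 1.7 × 0.387 × 0.1755/0.90 = 0.128; the simulation gave 0.132.

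**5. Against sampling error.** At ρ = 0.7 the residual SD is √(1−0.49) = 0.714. With 10% removed (18 v 20) the standard error is 0.714 × √(1/18 + 1/20) = 0.232, and the bias of 0.132 is 0.57 of it. With 20% removed (16 v 20) it is 0.714 × √(1/16 + 1/20) = 0.240, and the simulated bias of 0.237 is about one standard error.

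**6. Removal for non-compliance.** Taking the cited percentages as if they were removal rates, 20 × (1 − 0.22) = 15.6 and 20 × (1 − 0.49) = 10.2 iCST dyads would remain (49% is 100% − 51%). At ρ = 0.7 the bias is about 0 if compliance is unrelated to outcome. It is 0.08 or 0.16 SD if better compliance correlates 0.3 with better outcome given baseline. The effect on counts needs no such link: removing 22% of the iCST arm adds 4.4 drop-outs, or 4.4/40 = 11 percentage points of all randomised.

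**7. Effect on the next trial.** n per arm = 2 × (1.96 + 0.84)² × (SD/difference)². For an illustrative difference of 0.4 true SD, two-sided 5% and 80% power, the true SD gives 99 per arm. An SD 5% too low gives 89 and one 10% too low gives 80. At the extreme ratio of 0.77 (equal removal at 20%), 98.1 × 0.77² = 58.2, or 59 per arm.

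**The case against.** The wording is permissive. Participants *may* be withdrawn when that serves their interests, and the reasons *may* include those listed. A reader might infer that the plan deletes the worst outcomes by rule. It does not; it allows that to happen.

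A reader might also infer that follow-up certainly stops. The sentence on withdrawal from treatment, and the one tying an end to data to explicit refusal, allow the opposite reading. So does section 11.6.1, whose flow diagram counts completing the intervention separately from completing the final assessment. This stands, and it is why the point is one of inconsistent text and not of a settled plan to stop assessing.

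The calculation is harsh. It sorts participants perfectly on CAMCOG-DS change, whereas progression would be judged clinically. Loss confined to the iCST arm is an inference: controls could be withdrawn too, and at equal rates the bias in the difference vanishes. The 22% in the earlier trial is non-adherence in another population. It is neither a withdrawal nor a progression rate, and it cannot support any assumed removal fraction. The SD is imprecise in any case: on 37 degrees of freedom its relative standard error is about 1/√74 = 12%, more than the 4% to 9% understatement when only one arm loses participants. All of this stands, but the understatement has a direction and adds to the sampling error.

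Withdrawal reasons are recorded (8.6) and diaries count sessions (11.6.3), so non-adherence can be separated from drop-out if the report does so. The analysis set and missing-data method may be in an analysis plan not shown, and the protocol does not state that only completers are analysed. Section 11.6.4, however, is an explicit exclusion and not a silence.

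**Conclusion.** The concern holds as an inconsistency with a plausible statistical cost. Section 8.6 can be followed in a way that loses CAMCOG-DS values because of decline, more likely in the iCST arm, and 11.6.4 excludes the analysis that would show how much this matters.

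The size is unknown. Under the assumptions above, the bias towards iCST is about 0.05 to 0.28 outcome SD if only iCST participants are removed, and 0.02 to 0.12 SD if controls are removed at half the rate. At equal rates it is about 0, with the residual SD still at 0.77 to 0.92 of its true value. For non-compliance, bias in the difference arises only if compliance is related to outcome; the distortion of the drop-out count does not depend on that.

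The documents do not support saying that the estimate *is* biased, or that the missing data *will* depend on the outcome. Severity is moderate: there is no confirmatory test, and the harm falls on the planning figures and feasibility counts.

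**What to change.** - **Section 8.6:** reconcile the sentences on trial and on treatment by defining stopping iCST and leaving the trial separately. State that participants who stop iCST for progression or non-compliance remain in follow-up and are invited to both scheduled assessments, unless consent or consultee agreement for data collection is withdrawn or continued assessment is not in their best interests. When iCST itself is stopped stays as it is.
- **Section 11.6:** analyse participants as randomised, and report non-adherence separately from drop-out, by arm and with reasons.
- **Section 11.6.4:** replace the blanket exclusion with one simple missing-data sensitivity analysis for CAMCOG-DS, its form left to the trial statistician.

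The cost is a wording amendment and one extra analysis. The follow-up visits are already scheduled for all 40 participants. Some whose dementia has progressed may not manage the assessment, so some outcome-related missingness will remain; that is why the sensitivity analysis is needed as well as the wording.

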8.7 Definition of End of Trial

The expected duration of the trial is 18 months from recruitment of the first participant.

The end of trial is the date of the last home visit of the last participant taking part in the qualitative interviews.

9 Recording and reporting of adverse events

9.1 Definitions

Term	Definition					
Adverse Event (AE)	Any untoward medical occurrence in a patient or trial participant, which does not necessarily have a causal relationship with the intervention involved.					
Serious Adverse Event (SAE).	 Any adverse event that: results in death, is life-threatening*, requires hospitalisation or prolongation of existing hospitalisation**, results in persistent or significant disability or incapacity, or 					
	 consists of a congenital anomaly or birth defect. 					

^{*} A life- threatening event, this refers to an event in which the participant was at risk of death at the time of the event; it does not refer to an event which hypothetically might have caused death if it were more severe.

^{**} Hospitalisation is defined as an in-patient admission, regardless of length of stay. Hospitalisation for pre-existing conditions, including elective procedures do not constitute an SAE.

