9.2 Assessments of Adverse Events

Each adverse event will be assessed for severity, causality, seriousness and expectedness as described below.

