9.2.3 Expectedness

Category	Definition
Expected	An adverse event which is consistent with the information about the intervention listed in the SPC, manual of Operation (amend as appropriate) or clearly defined in this protocol.
Unexpected	An adverse event which is not consistent with the information about the intervention listed in the SPC, manual of Operation (amend as appropriate)* or clearly defined in this protocol.

^{*} This includes listed events that are more frequently reported or more severe than previously reported.

There are no known adverse effects of Cognitive Stimulation Therapy. However, taking part may possibly cause distress/ inconvenience for some participants with dementia

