9.3 Recording adverse events

All adverse events will be recorded with clinical symptoms and accompanied with a simple, brief description of the event, including dates as appropriate.

All adverse events will be recorded in the CRF until the participant completes the trial.

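### The SAE footnote in 9.1 excludes admissions for pre-existing conditions without separating planned admissions from unplanned ones for worsening, so the latter can drop to non-serious AEs

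*Protocol*

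**What the plan says.** The table in Protocol section 9.1 counts an adverse event as serious if, among other criteria, it "requires hospitalisation or prolongation of existing hospitalisation". A footnote attached to that criterion has two sentences. The first is broad: "Hospitalisation is defined as an in-patient admission, regardless of length of stay". The second takes a class of admissions out: "Hospitalisation for pre-existing conditions, including elective procedures do not constitute an SAE".

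The other seriousness criteria carry no such exclusion. An event that "results in persistent or significant disability or incapacity", is fatal or is life-threatening is an SAE whether or not the underlying condition was there at entry.

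The adverse event definition in the same table is wide: "Any untoward medical occurrence in a patient or trial participant, which does not necessarily have a causal relationship with the intervention involved". Section 9.3 adds "All adverse events will be recorded in the CRF until the participant completes the trial", and section 9.2 adds "Each adverse event will be assessed for severity, causality, seriousness and expectedness as described below".

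Section 9.5, the place for SAEs exempt from reporting, is marked not applicable.

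**The concern.** An exclusion for pre-existing conditions is reasonable when it removes admissions that were already arranged, or elective procedures for a stable problem. Those admissions say nothing about what happened to the participant during the trial. The footnote goes further. Elective procedures are named as an example of what is excluded, not as its limit, and nothing is said about a condition that gets worse or an admission nobody planned.

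That matters in this population because section 6.1 requires both dementia and a premorbid intellectual disability. Section 8.6 also expects that some participants' disease may progress during the trial, since it lists progression among the reasons for discontinuing. Unplanned admission for worsening of an existing condition is therefore a foreseeable event here.

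At stake is which reporting route such an admission takes. SAEs go to the sponsor and to the Trial Management Group on set timelines. Non-serious adverse events are recorded on the CRF and, as far as the protocol says, go no further in the safety chain.

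**Working it through.** The protocol gives no SAE rate, admission rate or safety-based sample size, so there is no figure to reproduce. The check is to follow one event through the text: a participant has an unplanned in-patient admission because an existing illness, such as dementia, has worsened. The admission is not life-threatening, and no death or lasting disability results.

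1. **Is it an adverse event?** Yes. The definition in 9.1 covers any untoward medical occurrence and does not exclude pre-existing conditions or their worsening.
2. **Does it meet the hospitalisation criterion?** On the table and the first sentence of the footnote, yes: any in-patient admission counts, however short.
3. **Does the exclusion remove it?** On a literal reading, yes. The admission is for a pre-existing condition. The footnote does not ask whether it was planned, whether the condition had worsened or whether the investigator thought the intervention was involved.
4. **Does another criterion bring it back?** Not in this example. It would if the event were fatal, life-threatening or permanently disabling.
5. **What happens to it then?** It is recorded on the CRF under 9.3 and assessed under 9.2, but as a non-serious event.

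The two routes compare as follows.

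| Step | Classed as SAE | Classed as non-serious AE |
|---|---|---|
| CRF entry (9.3) and assessment, including causality (9.2) | Yes | Yes |
| Site investigator to chief investigator within 48 hours (9.4) | Yes | No |
| SAE form to sponsor within 5 working days (9.4) | Yes | No |
| Report to the Health Research Authority within 15 days if unexpected and thought related (9.4, under SAE procedures) | Yes | Not provided for |
| Trial Management Group review (13.1) | Yes | Not mentioned |

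The exclusion also sits badly with two other sections. Section 9.2.2 stresses the importance of capturing events related to the therapy, yet the footnote operates whatever the causality assessment. Section 9.5 exempts no SAE from reporting, so a reader of 9.4 and 9.5 would believe that all serious admissions are reported, while 9.1 has already removed a class of them by definition.

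Finally, the text can be read in two ways. One site may treat a worsening as part of the pre-existing condition and apply the exclusion. Another may treat it as a new untoward event and report an SAE. The Summary names nine trusts, so inconsistent classification is a practical possibility.

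**The case against.** The strongest reply is that little is lost. All adverse events are recorded and assessed, Appendix 1 schedules adverse event reviews at visits, and section 10.3 has CRFs returned to the central team within two weeks of a visit. The gravest outcomes remain SAEs. The intervention is neither a drug nor invasive. The wording is also open enough for a sensible site to report an acute worsening as new. This stands in part: it limits the consequence to classification, timeliness and oversight. It does not answer the gap, because CRF entry does not trigger the 9.4 timelines or Trial Management Group review, and reliance on each site's reading makes the SAE count inconsistent.

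A reader might also draw stronger conclusions that the protocol does not support:

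- **That these admissions go unrecorded.** They do not: 9.2 and 9.3 apply to every adverse event.
- **That the trial's conclusion on tolerability is undermined.** Section 4 bases tolerability and acceptability on recruitment, willingness to be randomised, outcome measures, drop-out, adherence and acceptability. SAE counts are not among these, nor are they an outcome in 11.1 or 11.2.
- **That the excluded admissions are the ones most likely to be caused by the therapy.** Section 9.2.3 says only that "taking part may possibly cause distress/ inconvenience for some participants with dementia" and reports no known adverse effects. Section 3.1 has a distressing session stopped. Nothing links such distress to hospital admission.
- **That a particular number or share of SAEs would be lost.** Any such figure would need an admission rate and a proportion due to worsening, and the protocol gives neither.

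**Conclusion.** The point holds as a defect in a stated definition. The footnote in 9.1 does not separate elective or pre-planned admissions for a stable condition from unplanned admissions for worsening. As written, an admission of the second kind that meets no other seriousness criterion is a non-serious adverse event and misses the SAE form, the 9.4 timelines and Trial Management Group review of SAEs.

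Its size cannot be put in numbers. All 40 planned participants with dementia enter with at least two pre-existing conditions, so any of them could fall under the exclusion, but how many will be admitted for worsening is unknown. The conclusion rests on a literal reading of the footnote. On the more generous reading the problem becomes one of inconsistent classification between sites, which the same change would cure. It should be corrected, though it does not threaten the feasibility objectives.

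**What to change.** Reword the second sentence of the hospitalisation footnote in 9.1 so that the exclusion covers only elective admissions, or admissions planned before consent, for a condition that has not worsened since baseline. Add that an unplanned admission for worsening of a pre-existing condition remains an SAE under the hospitalisation criterion. Sections 9.4, 9.5 and 13.1 then work as they stand.

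The change concerns event classification only and alters nothing in participants' care. In a trial of 40 dyads the cost is the amendment itself and a few more SAE forms.

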9.2 Assessments of Adverse Events

Each adverse event will be assessed for severity, causality, seriousness and expectedness as described below.

9.2.1 Severity

The generic categories below are given for use as a guide.

Category	Definition
Mild	The adverse event does not interfere with the participant's daily routine, and does not require further intervention; it causes slight discomfort
Moderate	The adverse event interferes with some aspects of the participant's routine, or requires further intervention, but is not damaging to health; it causes moderate discomfort
Severe	The adverse event results in alteration, discomfort or disability which is clearly damaging to health

